3. OBJECTIVES AND ENDPOINTS

Objectives	Endpoints
Primary	

 To evaluate the ORR of apalutamide in combination with a GnRH agonist in participants with AR expressing locally advanced or recurrent/metastatic SGC 	
 ORR; the proportion of participants who are evaluated as confirmed CR or PR by an independent central radiology review based on RECIST version 1.1
Secondary	

 To evaluate the efficacy, PK, and safety endpoints or parameters with apalutamide plus a GnRH agonist in participants with AR expressing locally advanced or recurrent/metastatic SGC 	
 CBR; CR, PR, and SD for at least 24 weeks DCR; CR+PR+SD PFS OS TTR DOR Safety profile of apalutamide in combination with a GnRH agonist PK of apalutamide and its active metabolite (N-desmethyl apalutamide)
Exploratory	

 To evaluate effect of AR expression on apalutamide treatment in combination with a GnRH agonist 	
 ORR, CBR, DCR, PFS, OS, TTR, and DOR by AR-positivity

 To evaluate exploratory biomarkers predictive of response and resistance in participants when treated with apalutamide in combination with a GnRH agonist 	
 Biomarkers predictive of response and resistance to therapy such as AR, BRCA2, PTEN TP53, HRAS, PIK3CA, FOXA1, and ERBB2

 To explore the relationships between PK, AE profiles, and clinical activity of apalutamide in combination with a GnRH agonist 	
 Relationships between PK, AE profiles, and clinical activity of apalutamide in combination with a GnRH agonist. The relationship between PK and biomarkers may be evaluated if effective biomarkers such as PSA could be identified in the future for SGC

 To evaluate safety profile and effect on sex hormones (FSH, LH, E2) of apalutamide in combination with a GnRH agonist for female participants 	
 Safety profile of apalutamide in combination with a GnRH agonist for female participants

Key: AE=adverse event; AR=androgen receptor; CBR=clinical benefit rate; CR=complete response; DCR=disease control rate; DOR=duration of response; E2=estradiol; FSH=follicle stimulating hormone; GnRH=gonadotropin-releasing hormone; LH=luteinizing hormone; ORR=overall response rate; OS=overall survival; PFS=progression-free survival; PK=pharmacokinetic(s); PR=partial response; PSA=prostate-specific antigen; RECIST=Response Evaluation Criteria In Solid Tumors; SD=stable disease; SGC=salivary gland carcinoma; TTR=time to response.

Refer to Section 8, Study Assessments and Procedures for evaluations related to endpoints.

HYPOTHESIS

The primary hypothesis of this study is that apalutamide in combination with a GnRH agonist will demonstrate significant antitumor activity (ie, the number of responders is greater than or equal to the minimum number of responders for efficacy defined in Section 9.5) and an acceptable safety profile in participants with AR expressing locally advanced or recurrent/metastatic SGC.

4. STUDY DESIGN

4.1. Overall Design

This is an open-label, single-arm, multicenter, Phase 2 study to evaluate the efficacy and safety of apalutamide in combination with a GnRH agonist in participants with AR expressing locally advanced or recurrent/metastatic SGC.

A target of 24 participants will be included in this study and receive apalutamide and a GnRH agonist.

The study will consist of a screening phase, a treatment phase, and a follow-up phase. The study is anticipated to end approximately 42 months after the first participant is consented.

The study will be conducted in an outpatient setting and a treatment cycle is defined as 28 days. Study intervention will continue until disease progression, unacceptable toxicity, death, or the end of the study. Study intervention will be discontinued if a participant meets any of criteria described in Section 7.1, Discontinuation of Study Intervention.

After discontinuing study intervention, participants will be contacted every 6 months (refer to the SoA in Section 1.3) until death or the end of the study.

Participants will be monitored for safety starting from the signing of informed consent until 30 days after the last dose of study intervention. Adverse events including laboratory AEs will be graded and summarized using version 5.0 of the National Cancer Institute-Common Terminology Criteria for AEs (NCI-CTCAE). Dose modifications will be made as required according to dose modification rules (Section 6.6). An independent central radiology review will be used to reduce potential bias during data collection and evaluation of the primary endpoint of ORR and secondary endpoints including PFS (Section 9).

A diagram of the study design is provided in Section 1.2, Schema.

4.2. Scientific Rationale for Study Design

4.2.1. Blinding, Control, Study Phase/Periods, Intervention Groups

Randomization will not be used in this study. As this is an open-label Phase 2 study to evaluate the effect of apalutamide plus GnRH agonist on ORR, blinding procedures are not applicable.

4.2.2. Target Patient Population

Patients with AR-positive locally advanced or recurrent/metastatic SGC will be enrolled in this study. AR-positivity will be defined according to immunohistochemistry (IHC) staining of tumor tissue with at least 1% of cell nuclei staining positive. Given the reported high frequency of AR immunoreactivity and the potential therapeutic application of ADT in SDC, AR IHC becomes a widely-used diagnostic marker and a possible predictive biomarker for these patients. Variable criteria were utilized to define positive AR expression in previous studies ranging from any nuclear staining to diffuse nuclear staining. However, the published frequency of AR immunopositivity in SDC was not drastically affected by such variability, since the majority of SDCs show diffuse and strong AR staining. Several studies have used a cutoff of any positivity to $\geq 1\%$ positive tumor cell nuclei, and have reported a frequency of AR-positivity ranging from 75% to 100% while some other studies did require strong and/or diffuse nuclear staining to consider AR-positive, and reported an AR-positivity rate ranging from 69% to 100%.⁶³

4.2.3. Treatment Regimen

Participants will be treated with apalutamide in combination with GnRH agonist. As for monotherapy with antiandrogen, the rise in tumor-associated testosterone following enzalutamide monotherapy has previously been reported in prostate cancer and increased testosterone could outcompete the antiandrogen monotherapy and recover AR activation.^{2,14} Actually, in AR-positive SGC or specific subtype of SDC patients, while Ho et al and Jaspers et al reported low ORRs of 4.3% to 20% treated with enzalutamide or bicalutamide monotherapy,^{22,27} Fushimi et al and Locati et al reported an ORR of 41.7% and 64.7%, respectively, with bicalutamide in combination with a GnRH agonist,^{18,35} suggesting that CAB may improve response rates compared with antiandrogen monotherapy.

4.2.4. Justification for Dose

Dosage of apalutamide investigated in this study will be 240 mg once daily, which is same as the recommended clinical dose for prostate cancer. The dosage was selected based on the plateaued AR binding observed in the 16β -[¹⁸F]fluoro- α -dihydrotestosterone-positron emission tomography (FDHT-PET)/computed tomography (CT) study in CRPC patients (at doses above 120 mg), combined with the fact that plasma trough concentration of apalutamide at 240 mg in CRPC patients are expected to well exceed the concentration in CRPC mouse model showing maximum tumor regression.⁵⁰ Also, previous studies demonstrated prominent ORRs in SGC with the same doses and administration of bicalutamide and a GnRH agonist as that approved for prostate cancer in each regions.^{18,35} With these considerations, 240 mg taken orally once daily was selected in this study.

4.3. End of Study Definition

End of Study Definition

The end of study is considered as the last scheduled study assessment shown in the SoA (Section 1.3) for the last participant in the study, the decision of termination by the sponsor or regulatory authorization. Enrolled participants will be transitioned from study intervention to commercial product once commercial product is available by a doctor's prescription.

Study Completion Definition

A participant will be considered to have completed the study if he or she has died before the end of the study, has been lost to follow-up, or withdrawn consent before the end of the study.

5. STUDY POPULATION

Screening for eligible participants will be performed within 28 days before administration of the study intervention. Refer to the note at the end of Section 5.2, Exclusion Criteria for conditions under which the repeat of any screening procedures are allowed.

The inclusion and exclusion criteria for eligibility in this study are described below. If there is a question about these criteria, the investigator must consult with the appropriate sponsor representative and resolve any issues before initiating the study intervention in the study. Waivers are not allowed.

For a discussion of the statistical considerations of participant selection, refer to Section 9.2, Sample Size Determination.

5.1. Inclusion Criteria

Each potential participant must satisfy all of the following criteria to be eligible for the study:

1. Man or woman ≥ 18 years of age
2. Histologically confirmed SGC by local pathology
3. AR expressing SGC: Local testing of AR-positivity will be performed as standard of care for the eligibility confirmation. AR-positivity will be defined according to IHC staining of tumor tissue with at least 1% of cell nuclei staining positive. Tissue should be available for the central confirmation of AR-positivity, but the central result of AR-positivity will not be required for initiating the study intervention
4. Locally advanced or recurrent/metastatic SGC fulfilling at least 1 of the following conditions:
 - a. Primary lesion of T4b (Union for International Cancer Control [UICC]/TNM, 8th edition)
 - b. Cervical lymph node metastasis of N2c, N3a or N3b (UICC/TNM, 8th edition)
 - c. Unresectable lesion equivalent to the condition of 'a' or 'b' above in case of recurrence
 - d. Distant metastasis
5. Measurable lesion(s) according to the RECIST version 1.1
6. Eastern Cooperative Oncology Group (ECOG) performance status 0, 1 or 2

7. Clinical laboratory values at screening:
 - a. Hemoglobin ≥ 8.0 g/dL, independent of transfusion and/or growth factors within 1 month prior to first dose
 - b. Platelet count $\geq 75,000/\mu\text{L}$ independent of transfusion and/or growth factors within 1 month prior to first dose
 - c. Serum albumin ≥ 3.0 g/dL
 - d. Serum creatinine $< 2.0 \times$ institutional upper limit of normal (ULN)
 - e. Serum total bilirubin $\leq 1.5 \times$ ULN (Note: In participants with Gilbert's syndrome, if total bilirubin is $> 1.5 \times$ ULN, measure direct and indirect bilirubin and if direct bilirubin is $\leq 1.5 \times$ ULN, participant may be eligible)
 - f. Aspartate aminotransferase (AST) or alanine aminotransferase (ALT) $< 2.5 \times$ ULN or $\leq 5.0 \times$ ULN for participants with liver metastases

8. A woman of childbearing potential:
 - a. must have a negative pregnancy test (β -human chorionic gonadotropin [β -hCG]) at screening (urine or serum)
 - b. must agree not to breast-feed during the study and for 3 months after the last dose of study intervention
 - c. must agree not to donate eggs (ova, oocytes) for the purposes of assisted reproduction during the study and for 3 months after the last dose of study intervention
 - d. must not plan to become pregnant during the study and for 3 months after the last dose of the study intervention and practice effective method(s) of birth control as described below:
 - Practicing true abstinence (when this is in line with the preferred and usual lifestyle of the participant), which is defined as refraining from heterosexual intercourse during the entire period of the study, including up to 3 months after the last dose of study intervention. Periodic abstinence (calendar, symptothermal, postovulation methods) is not considered an acceptable contraceptive method, or
 - Have a sole partner who is vasectomized, and he must still use a condom, or
 - Practicing 2 contraceptive methods and one must be user-independent method. Examples of highly effective contraceptives approved in Japan include:
 - ◆ User-independent methods: intrauterine device or intrauterine contraceptive system
 - ◆ User-dependent methods: oral combined (estrogen- and progestogen-containing) hormonal contraception

- e. Participants must agree to continue contraception throughout the study and continuing through 3 months after the last dose of study intervention

Note: If the childbearing potential changes after start of the study (eg, woman who is not heterosexually active becomes active), the woman must begin a highly effective method of birth control, as described above.

9. A woman not of childbearing potential: postmenopausal (>45 years of age with amenorrhea for at least 12 months [a woman should still be considered of childbearing potential if amenorrhea is due to a medical reason, eg, drug induced amenorrhea]); permanently sterilized (eg, bilateral tubal occlusion [which includes tubal ligation procedures as consistent with local regulations], hysterectomy, bilateral salpingectomy, bilateral oophorectomy); or otherwise be incapable of pregnancy.
10. A man who is sexually active with a woman of childbearing potential must agree to continue contraception throughout the study including up to 3 months after the last dose of study intervention. He must use a condom and his partner must also be practicing a highly effective method of contraception (ie, established use of oral combined hormonal methods of contraception; placement of an intrauterine device or intrauterine system).

If the participant is vasectomized, he must still use a condom, but his female partner is not required to use contraception.
11. Willing and able to adhere to restrictions (Sections 5.3 and 6.5, and Appendix 8 [Section 10.8]) specified in this protocol.
12. Be able to swallow the study intervention tablets whole
13. Must sign an ICF indicating that he or she understands the purpose of, and procedures required for, the study and is willing to participate in the study

5.2. Exclusion Criteria

Any potential participant who meets any of the following criteria will be excluded from participating in the study:

1. Treatment with any other investigational agent or participation in another clinical study with therapeutic intent within 30 days prior to first dose. Treatment with a drug that has a short $t_{1/2}$ (for example, <1 day) may be eligible in accordance with the discussion with the sponsor's medical monitor
2. Radiographically confirmed brain metastases. In case of history of brain metastases that were previously treated and not recurred for at least 6 months, they are considered eligible

3. Criterion modified per Amendment 1

3.1. Received prior ADT including a GnRH analogue, AR blocker such as bicalutamide, enzalutamide or 17alpha-hydroxylase-17,20-lyase (CYP17) inhibitor such as abiraterone acetate etc. Chemotherapy, radiation, or surgery as part of curative intent therapy are allowed so long as prior therapy did not include ADT. If patients with T4b received prior radiation and progressed, they are excluded.

Prior chemotherapy, targeted cancer therapy or immunotherapy within 1 week or 4 half-lives whichever is longer, before the first administration of study drug. For agents with long half-lives, the maximum required time since last dose is 2 weeks.

4. Criterion modified per Amendment 1

4.1. Toxicities from previous anticancer therapies should have resolved to baseline levels or to Grade 1 or less (except for all grade alopecia and for peripheral neuropathy, and hypothyroidism stable on hormone replacement therapy to be Grade 2 or less).

If corticosteroids are administered for any reasons such as the management of toxicities due to prior therapies, the dose must be tapered until 10 mg/day or less of prednisolone and contact the sponsor's medical monitor on an individual basis prior to the first dose.

5. Any of the following within 6 months prior to first dose of study intervention: severe or unstable angina, myocardial infarction, symptomatic congestive heart failure, arterial or venous thromboembolic events (eg, pulmonary embolism, cerebrovascular accident including transient ischemic attacks), or clinically significant ventricular arrhythmias or New York Heart Association Class II to IV heart disease; uncomplicated deep vein thrombosis is not considered exclusionary

6. Human immunodeficiency virus-positive participants with 1 or more of the following:

- a. Not receiving highly active antiretroviral therapy
- b. Had a change in antiretroviral therapy within 6 months of the start of screening
- c. Receiving antiretroviral therapy that may interfere with study intervention (consult sponsor for review of medication prior to initiation of the study intervention)
- d. CD4 count <350/ μ L at screening, if available
- e. Acquired immunodeficiency syndrome (AIDS)-defining opportunistic infection within 6 months of start of screening

7. Active or symptomatic viral hepatitis or chronic liver disease; ascites or bleeding disorders secondary to hepatic dysfunction

8. History of seizure or any condition that may predispose to seizure (including, but not limited to, prior stroke, transient ischemic attack, or loss of consciousness \leq 1 year prior

to first dose; brain arteriovenous malformation; or intracranial masses such as schwannomas and meningiomas that are causing edema or mass effect)

9. Treatment with drugs known to lower the seizure threshold within 4 weeks prior to first dose (Sections 6.5.3 and 10.8 [Appendix 8])
10. Gastrointestinal conditions with evidence of major malabsorption
11. Known or suspected contraindications or hypersensitivity to apalutamide, GnRHa analogues or any of the components of the formulations
12. Any condition for which, in the opinion of the investigator, participation would not be in the best interest of the participant
13. Active malignancies (ie, requiring treatment change in the last 24 months). The only allowed exceptions are:
 - a. Non-muscle invasive bladder cancer (NMIBC)
 - b. Skin cancer treated within the last 24 months prior to the first dose that is considered completely cured
 - c. Localized prostate cancer with a Gleason score of 6 (treated within the last 24 months or untreated and under surveillance)
 - d. Localized prostate cancer with a Gleason score of 3+4 that has been treated more than 6 months prior to first dose and considered to have a very low risk of recurrence
 - e. Non-invasive cervical cancer treated within the last 24 months that is considered completely cured
 - f. Breast cancer: adequately treated lobular carcinoma in situ or ductal carcinoma in situ, or history of localized breast cancer and receiving antihormonal agents and considered to have a very low risk of recurrence

Contact the sponsor's medical monitor in case of any ongoing anticancer therapies

14. Criterion added per Amendment 1

Any history of Interstitial lung disease (ILD) or conditions that may predispose to ILD including, but not limited to, breath shortness, dyspnoea, cough and fever with signs of ILD by CT.

NOTE: Investigators should ensure that all study eligibility criteria have been met at screening. Retesting of abnormal results such as laboratory value that may lead to exclusion will be allowed once. Also, if a participant's clinical status changes (including any available laboratory results or receipt of additional medical records) after screening but before the first dose of study intervention is given such that he or she no longer meets all eligibility criteria, supportive treatment may be administered, if necessary, so that eligibility criteria can be met. In the case, laboratory test(s) will

be repeated once, to determine if the participant qualifies for the study again. If eligibility criteria are not met after further evaluation (retesting), the participant should be excluded from participation in the study. Contact the sponsor's medical monitor discuss if further evaluation is acceptable in advance if the investigator believes that it is in the best interest of the participant.

Participants will be allowed to be rescreened only once for eligibility after initial screen failure if the investigator has a valid reason (eg, true resolution of conditions previously meeting the exclusion criteria) to rescreen and after consultation with the medical monitor. Participants who are to be rescreened must sign a new ICF before rescreening. The previous screening results including laboratory tests, and CT/MRI etc may be used to determine eligibility if they were performed within 28 days of planned first dose. Rescreening and subsequent study activities must be conducted in accordance with all protocol-defined windows and timelines. The required source documentation to support meeting the eligibility criteria are noted in Section 10.3, Appendix 3, Regulatory, Ethical, and Study Oversight Considerations.

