1.3. Schedule of Activities (SoA)

Phase	Screening	Treatment									Follow-up ^e	Notes	
		Cycle 1			Cycle 2		Cycle 3	Cycles 4-6	Cycle 7 until EOT	EOT			
CYCLE (defined as 28 days)	Within 28 days before CID1, unless otherwise specified												
CYCLE DAY		Day 1	Day 8 (±1 day)	Day 15 (±1 day)	Day 1	Day 15	Day 1	Day 1	Day 1	Day 1	Within 30 days after last dose	Every 6 months (±14-day)	Unless otherwise specified, study visits/procedures have a ±2-day time window
Screening													
Informed consent (ICF) ^a	X												Must sign the ICF before first study-related activity.
Medical history and demographics, including any prestudy therapy for SGC	X												
Inclusion/exclusion criteria	X	X											
Urine or serum β-hCG pregnancy test	X 7 days	As clinically indicated, by urine or serum test											Women of childbearing potential only. Screening test within 7 days of first dose.
Study Intervention Administration													
Dispense apalutamide		X			X		X	X	X				Apalutamide and GnRH agonist will be administered according to Section 6.1, Study
Dispense and administer GnRH agonist		X			X		X	X	X				

Phase	Screening	Treatment									Follow-up ^c	Notes
		Cycle 1			Cycle 2		Cycle 3	Cycles 4-6	Cycle 7 until EOT	EOT		
CYCLE (defined as 28 days)	Within 28 days before C1D1, unless otherwise specified	Cycle 1			Cycle 2		Cycle 3	Cycles 4-6	Cycle 7 until EOT	EOT	Follow-up	
CYCLE DAY		Day 1	Day 8 (±1 day)	Day 15 (±1 day)	Day 1	Day 15	Day 1	Day 1	Day 1	Within 30 days after last dose	Every 6 months (±14-day)	Unless otherwise specified, study visits/procedures have a ±2-day time window
												Interventions Administered.
Dose compliance					X		X	X	X	X		Includes a tablet count (refer to Section 6.4).
Efficacy Evaluations^b												
CT or MRI (neck, chest, abdomen, and pelvis)	X						X	X	X		(X) ^c	Screening, Cycles 3, 5, 7, 9, 11 then q3 cycles beginning at Cycle 13. The same modality (CT or MRI) should be used throughout the study. Imaging visits may occur up to 7 days before cycles requiring images. Unscheduled assessments may be performed if signs of disease

Phase	Screening	Treatment									Follow-up ^e	Notes
		Cycle 1			Cycle 2		Cycle 3	Cycles 4-6	Cycle 7 until EOT	EOT		
CYCLE (defined as 28 days)	Within 28 days before C1D1, unless otherwise specified	Cycle 1			Cycle 2		Cycle 3	Cycles 4-6	Cycle 7 until EOT	EOT	Follow-up	

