4.3.1 Evaluation of target lesions

Complete Response (CR): Disappearance of all target lesions. Any pathological lymph nodes (whether target or non-target) must have reduction in short axis to < 10 mm.

Partial Response (PR): At least a 30% decrease in the sum of diameters of target lesions, taking as reference the baseline sum diameters.

Progressive Disease: At least a 20% increase in the sum of diameters of target lesions, taking as reference the smallest sum on study (this includes the baseline sum if that is the smallest on study). In addition to the relative increase of 20%, the sum must also demonstrate an absolute increase of at least 5 mm. (Note: the appearance of one or more new lesions is also considered progression).

Stable Disease (SD): Neither sufficient shrinkage to qualify for PR nor sufficient increase to qualify for progressive disease, taking as reference the smallest sum diameters while on study.

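### The RECIST baseline scan is not tied to the last dose of prior therapy and may precede it by up to about 21 days, so some shrinkage from that therapy could be credited to study treatment.

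*Protocol*

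**What the plan says.** **Washout.** Protocol 5.2, criterion 3.1 excludes "Prior chemotherapy, targeted cancer therapy or immunotherapy within 1 week or 4 half-lives whichever is longer, before the first administration of study drug". The next sentence caps the requirement: "For agents with long half-lives, the maximum required time since last dose is 2 weeks". Both are counted from the first study dose.

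**Baseline scan.** Protocol 5 states: "Screening for eligible participants will be performed within 28 days before administration of the study intervention". The Schedule of Activities (Protocol 1.3) puts CT/MRI in a screening column headed "Within 28 days before C1D1, unless otherwise specified", and its imaging note sets no shorter limit for the screening scan. At rescreening, earlier CT/MRI "may be used to determine eligibility if they were performed within 28 days of planned first dose" (note to Protocol 5.2).

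**Use of the baseline.** Protocol Appendix 9 defines partial response as "At least a 30% decrease in the sum of diameters of target lesions, taking as reference the baseline sum diameters". SAP 2 takes the closest pre-dose measurement as baseline.

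**Related rules.** Investigational agents have their own limit: "Treatment with any other investigational agent or participation in another clinical study with therapeutic intent within 30 days prior to first dose", although that criterion allows short half-life drugs after discussion with the sponsor. Prior systemic therapy is allowed, and SAP 2.3 plans a subgroup by 0 versus at least 1 prior line. The inclusion criteria require measurable disease but not progression on the latest therapy. The primary estimand (SAP 5.2.1) names only subsequent therapy as an intercurrent event. The one ORR sensitivity analysis (SAP 5.4.1) changes who reads the scans and keeps the same baseline.

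**The concern.** Response is a change from a reference measurement, so the reference should reflect the tumour after prior treatment has ended. Here the scan and the washout are each counted back from first dose and never compared with each other. A participant can be scanned, receive another dose or more of the prior regimen, complete the washout and start study treatment. If the tumour was shrinking on that regimen, the baseline sum is larger than the tumour burden at first dose, and part of the 30% fall needed for partial response has already happened.

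The trial has no control arm in which the same effect would appear, and the decision rests on 8 responders among 24. The amendment history says the washout was added to reduce the effect of prior cancer therapies, so carry-over was recognised, but the measurement from which response is judged was left outside that protection.

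**Working it through.** **1. The permitted gap.** Inputs: scan window 28 days (Protocol 1.3 and 5); minimum washout 7 days and cap 14 days (Protocol 5.2, criterion 3.1).

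Largest gap = scan window − required washout.
- Agents whose 4 half-lives are 7 days or less: 28 − 7 = 21 days (20 if Day −7 itself counts as within the week).
- Agents at the 2-week cap: 28 − 14 = 14 days.
- Agents in between: 14 to 21 days.
- Investigational agents under the 30-day rule: 28 − 30 is negative, so no gap.

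The 21 days comes from the 1-week rule. The 2-week cap alone gives 14.

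**2. Reproducing the plan's error rates.** Inputs from Protocol 9.5, Table 3: 12 then 24 participants; stop for futility at 1 or fewer responders of 12; efficacy at 7 or more of 12, or 8 or more of 24. With X1 and X2 the responders in each half:

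P(success) = P(X1 ≥ 7) + Σ (x = 2 to 6) P(X1 = x) · P(X2 ≥ 8 − x)

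- At 14%: 0.00044 + 0.01287 = 0.0133, matching the stated 1.3%.
- At 40%: 0.1582 + 0.6472 = 0.8054, matching the stated 80.5%.

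**3. Sensitivity to a raised apparent response rate.** The documents give no carry-over frequency, so these rates are assumptions.

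| Apparent null ORR | Interim term | Final term | Type I error |
|---|---|---|---|
| 14% | 0.0004 | 0.0129 | 1.3% |
| 15% | 0.0007 | 0.0191 | 2.0% |
| 16% | 0.0010 | 0.0272 | 2.8% |

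The 2.5% level is passed at about 15.6% (0.1565 to four decimals). That is (0.1565 − 0.14) × 24 ≈ 0.4 of an extra apparent responder on average.

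**4. What would produce such a rise.** Let f be the share of participants whose scan preceded their last prior dose, and q the chance that one of them who would not otherwise respond is nevertheless counted as a confirmed responder. Then the apparent rate is 0.14 + f × 0.86 × q.
- f = 5%, q = 10%: 0.1443, type I error 1.6%.
- f = 10%, q = 20%: 0.1572, type I error 2.6%.
- f = 20%, q = 20%: 0.1744, type I error 4.5%.

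The range runs from negligible to material, and the documents give no basis for choosing a point within it.

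**The case against.** **Other text may already close the gap.** Protocol 6.5.3 prohibits antitumour agents while on study, and the note to 5.2 asks that eligibility be met at screening. If a participant is on study from consent, a dose of prior therapy after the study scan is barred. This reading is possible, but criterion 3.1 counts expressly from first administration, and neither text orders the scan after the last prior dose. Appendix 9 advises screening evaluations as close as possible to treatment start, but sets no day limit and does not mention prior therapy. The SAP baseline rule selects the early scan when it is the only one. The rescreening note concerns eligibility and does not name the re-used scan as the RECIST baseline, so it supports the point only indirectly.

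**Confirmation narrows the problem.** This stands. Scheduled scans fall at Cycle 3 Day 1 (Day 57, or Day 50 with the 7-day allowance) and Cycle 5 Day 1 (Day 113, or Day 106). With a last prior dose 7 days before first dose, a response confirmed on scheduled scans must still be present at least 105 + 7 = 112 days after that dose. Extra scans could shorten this. Shrinkage that persists would still be confirmed, because both readings use the same early baseline.

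**The bias need not be upward.** This also stands. If the tumour grew between the scan and first dose, the baseline sum is too small and response is harder to reach. A reader might infer that the rule inflates ORR overall. The documents do not support that: upward bias arises only for participants still shrinking on a regimen they then stopped.

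**The size is chosen.** True: no rise of 1 or 2 points has a source in the documents, and a 1-point rise stays below 2.5%. One wrongly credited responder would turn 7/24 (single-stage p = 4.1%) into 8/24 (p = 1.3%), but that fragility belongs to any boundary at this sample size and says nothing about how often carry-over occurs.

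**Existing outputs help.** ORR by prior lines, if numbers suffice, and the individual response listings could flag suspect cases. Neither isolates participants whose scan preceded their last prior dose.

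**Conclusion.** The gap is real and rests on the text alone: the rules permit a baseline scan up to about 21 days before the last prior dose for short half-life agents, and 14 days at the cap. It concerns only participants coming directly from chemotherapy, targeted therapy or immunotherapy. Within that group, upward bias needs a tumour still shrinking on the stopped regimen and a fall that lasts through confirmation.

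A reader might go further and conclude that the trial's type I error exceeds 2.5%. That does not follow. The frequency and the net direction are unknown, and 2.0% at 15% and 2.8% at 16% are illustrations under assumed rates. They show that the margin above the stated 1.3% is used up by an apparent rise of about 1.6 points (15.6 − 14), which is enough reason to close the gap when closing it is cheap.

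**What to change.** 1. In the imaging note of the Schedule of Activities (Protocol 1.3), state that the baseline RECIST scan must be done after the last dose of prior anticancer therapy and within the existing 28-day window. Repeat this in the rescreening note of 5.2 for any re-used scan that serves as baseline. The washout length, sample size and boundaries stay as they are.

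2. For participants already enrolled, add to SAP 5.4 an ORR sensitivity analysis on the same fixed participants, counting as non-responders those whose baseline scan preceded their last prior dose, and report how many there are. It is deliberately conservative, since it also removes any genuine responders in that group, and it should not replace the primary decision rule.

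Cost: an occasional delay to entry or a repeat scan for participants imaged before their last prior dose, and one more line of analysis. Prestudy SGC therapy is already recorded at screening; the only added need is to check that last-dose dates are captured.
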